The selection of participants who have used cannabis, but are not current frequent users allows us to recruit individuals familiar with the effects of THC without issues of high levels of THC tolerance that might be present in daily users that could impact study outcomes. Any participant that reports having had an adverse reaction to cannabis that resulted in seeking medical treatment will be excluded.

Participant recruitment. Participants will be recruited into the study via media advertising (e.g. newspaper, internet) and word-of-mouth communication. Advertisements will seek healthy adults who occasionally use cannabis and are not currently trying to quit. Interested participants will receive an initial screening over the telephone, that includes interviews and self-report questionnaires that provide participant information regarding health status including physical, mental health, recreational drug use history, and experience of adverse effects following cannabis use, to determine eligibility for all criteria except those which require physical evaluation. Individuals who meet initial eligibility criteria will then be scheduled for an in-person physical evaluation.

Prior to the in-person assessment, written informed consent to participate in the study will be obtained. Urine specimens will be obtained and tested for evidence of recent use of commonly abused drugs. Participants must provide a government-issued photo ID confirming they are 18-55 years old, report prior use of cannabis, including at least 5 times in the past year, and report no allergies to cannabis or any of the test materials (e.g., products containing pinene or related substances such as turpentine). The physical exam will include clinical chemistry, hematology, serology, and serum pregnancy (females only) testing. Those who appear eligible for participation will receive training on study assessment measures (e.g. exposure to subjective questionnaires and cognitive performance tasks), as well as instruction on using the Mighty Medic vaporizer. Participants who successfully complete training and demonstrate competency on all performance measures will be invited to participate in the study.

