Experimental Session Procedures. For all study sessions, participants will be scheduled to arrive at approximately 8:00 in the morning on the day of cannabis exposure. Until such time as Covid-19-related restrictions on day-to-day operations are no longer required, social distancing will be maintained to the extent possible and all staff and study participants will be required to wear PPE throughout all face-to-face interactions. This will include mandatory use of face

masks and, when closer than 6ft, use of face shields and disposable gloves. Participants will be provided PPE by study staff as necessary.

All participants will complete a breath alcohol test on arrival. Urine drug and pregnancy testing will then be conducted for all participants to test for evidence of recent illicit drug use (e.g. cannabis, cocaine, opioids) and pregnancy. Participants with a positive BAL or urine drug screen positive for any drug except THC will be sent home and the session re-scheduled. Participants who have a 2nd positive BAL, 2nd positive urine drug screen or confirmed positive pregnancy test will be immediately discharged from the study. The Time Line Follow Back (TLFB) procedure will be conducted to record substance use since the last study visit (intake assessment or prior experimental session). Concomitant medications, including vitamins and herbal supplements taken within 14 days prior to the first experimental session and throughout study participation will be recorded. Changes in medication occurring between the screening assessment and first experimental session, or between subsequent experimental sessions will be reviewed by a study investigator and medical staff prior to starting the session to ensure the volunteer is still eligible to participate.

Baseline Assessments. Prior to drug administration, the following baseline assessments will be completed: 5mL serum blood sample, vital signs (HR, BP), subjective drug effect questionnaire, and a brief cognitive performance battery including tests of working and episodic memory (see below for details).

Experimental Drug Exposure.

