effect" on the most recent subjective drug effect assessment, performance on the cognitive test battery, and conduct a brief interview with the participant prior to discharge. At the end of each session, study staff will compare vital signs and cognitive performance assessments with baseline data and engage in face-to-face conversation with the participant to ensure that they are fit to leave the unit. Cognitive performance tasks obtained measure psychomotor ability, working memory, higher-order cognitive functioning and attention. If the participant is able to cognitively engage with staff, vital signs are within normative range (HR < 100bpm, SYS BP < 150mmHg, DIA BP < 90mmHg), and performance is not below 20% of baseline, the participant will be cleared to leave without further evaluation. If any of these parameters are not met, medical staff will assess the participant and a formal field sobriety test will be conducted. Note, that multiple members of the BPRU cannabis lab have received formal training on administering filed sobriety tests by a Maryland State Police Drug Recognition Expert (DRE). If the participant reports a drug effect or exhibits behavior indicative of impairment/intoxication, the participant will be asked to remain at the BPRU until the drug effect subsides and they can pass a field sobriety test. If vital signs are out of range, then medical staff will evaluate and make a determination with regards to whether it is safe for participant to be discharged or remain under observation. Participants will not be allowed to drive home; instructions will be provided at the screening session regarding the need to make alternative transportation arrangements. If a participant fails to arrange a ride, taxi transportation home will be coordinated by study staff and provided free of charge.

For ease of scheduling, we will target conduct of sessions on a weekly basis. Because there are 6 total sessions, some participants may want to complete at an accelerated rate. A minimum of 48 hours will separate each study session and no more than 2 sessions will be completed in a calendar week. These timing parameters will allow for adequate elimination of study drugs between sessions and keeps the frequency of exposure to acceptable levels given that the study population will be infrequent cannabis users at the time of study participation.

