- 4. Test negative for drugs of abuse other than cannabis, including breath alcohol at the screening visit and at clinic admission
- 5. Not be pregnant or nursing (if female). All females must have a negative serum pregnancy test at the screening visit and a negative urine pregnancy test at clinic admission.
- 6. Have a body mass index (BMI) in the range of 18 to 36 kg/m2
- 7. Blood pressure at Screening Visit does not exceed a systolic blood pressure (SBP) of 150 mmHg or a diastolic blood pressure (DBP) of 90 mmHg
- 8. Have no allergies to any of the ingredients used to prepare vapor (THC, pinene).
- 9. Demonstrate competency on cognitive performance measures at screening visit (e.g., PASAT score of 75/90).

Exclusion Criteria

- 1. Non-medical use of psychoactive drugs other than, nicotine, alcohol, or caffeine 3 month prior to the Screening Visit;
- 2. History of or current evidence of significant medical (e.g. seizure disorder) or psychiatric illness (e.g. psychosis) judged by the investigator to put the participant at greater risk of experiencing an adverse event due to exposure or completion of other study procedures.
- 3. Use of an OTC, systemic or topical drug(s), herbal supplement(s), or vitamin(s) within 14 days of experimental sessions; which, in the opinion of the investigator or sponsor, will interfere with the study result or the safety of the subject.
- 4. Use of a prescription medication (with the exception of birth control prescriptions) within 14 days of experimental sessions; which, in the opinion of the investigator or sponsor, will interfere with the study result or the safety of the subject.
- 5. Use of dronabinol (Marinol®) within the past month.
- 6. Average use of cannabis more than 2 times per week in the prior 3 months.
- 7. History of clinically significant cardiac arrhythmias or vasospastic disease (e.g., Prinzmetal's angina).
- 8. Enrolled in another clinical trial or have received any drug as part of a research study within 30 days prior to dosing.
- 9. Having previously sought medical attention to manage adverse effects following acute cannabis use.
- 10. Individuals with anemia or who have donated blood in the prior 30 days

[figure not shown]
6. Drugs/ Substances/ Devices

a. The rationale for choosing the drug and dose or for choosing the device to be used.

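### No arrival action or analysis rule covers recent non-study cannabis use, so a session, including placebo or pinene alone, can start soon after a participant's own use

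*Combined protocol and SAP*

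**What the plan says.** **Arrival check (section 4.a, Experimental Session Procedures).** Urine is tested "to test for evidence of recent illicit drug use (e.g. cannabis, cocaine, opioids) and pregnancy", so cannabis is among the drugs looked for. The action rule then leaves it out: "Participants with a positive BAL or urine drug screen positive for any drug except THC will be sent home and the session re-scheduled". The discharge rule that follows does not repeat the exemption: "Participants who have a 2nd positive BAL, 2nd positive urine drug screen or confirmed positive pregnancy test will be immediately discharged from the study".

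**Own use between visits.** "The Time Line Follow Back (TLFB) procedure will be conducted to record substance use since the last study visit". No threshold or consequence follows. Changes in medication, by contrast, must be reviewed by an investigator and medical staff before the session starts.

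**Who is enrolled.** The recruitment text seeks occasional users who are not trying to quit and who report at least 5 uses in the past year. Exclusion criterion 6 sets the upper limit: "Average use of cannabis more than 2 times per week in the prior 3 months". That is a limit on use before entry. The reviewed text sets none for use during the study.

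**Spacing of sessions.** At least 48 hours separate sessions, justified thus: "These timing parameters will allow for adequate elimination of study drugs between sessions". Only study drugs are mentioned.

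**What is collected.** "Prior to drug administration, the following baseline assessments will be completed: 5mL serum blood sample, vital signs (HR, BP), subjective drug effect questionnaire", together with a cognitive battery. Study Measures says that THC and its metabolites will be quantified.

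**Analysis (Study Statistics).** The primary outcome is total correct on the PASAT. Repeated-measures regression is planned, its form depending on the final data. Nothing is said about pre-dose values, TLFB use or pre-dose THC.

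**The concern.** THC is both the manipulated variable and the impairing agent, and the trial recruits people who use it. The protocol already treats outside exposure as relevant: it excludes recent dronabinol, and it restricts habitual use so as to work "without issues of high levels of THC tolerance that might be present in daily users that could impact study outcomes". Yet as written, a participant who reports own use that morning goes on to be tested, in whichever condition is due.

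Four things are at stake:

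- **Primary outcome.** Each condition is normally tested once per participant, so residual impairment in a session adds error to that participant's contrasts.
- **THC versus placebo.** If the residual lowers placebo scores more than THC scores, this difference shrinks. It is the deficit that pinene is meant to reduce.
- **Pharmacokinetics.** Objective 1 includes them. Carry-in can only raise measured THC and metabolites. Randomization spreads the rise over conditions but does not remove it.
- **Returning participants.** Earlier completers come back later for 15 mg pinene and for 30 mg THC + 15 mg pinene. For them these sessions follow the others by design, so a change in outside use over time is not balanced.

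**Working it through.** **1. The plan's own figure.** Study Statistics calls 20 completers adequate for an effect size of about 0.87 to 1.0. It gives no alpha, sidedness or power, so 20 cannot be strictly reproduced. With a paired t-test at two-sided 5% (my assumption), power at n = 20 is 95.8% for d = 0.87 and 98.9% for d = 1.0.

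**2. How often a session could follow own use.** The inputs are 5 uses per year (Participant recruitment), 2 uses per week (exclusion criterion 6) and 20 × 6 = 120 sessions. I assume that use continues at the entry rate, on separate occasions, at times unrelated to sessions. The 24-hour window is illustrative. The 6-hour window comes from Outpatient Discharge, which says about 6 hours has been enough for the effects of similar doses to resolve.

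| Window | Rate | Chance per session, p | Of 120 sessions | At least one of the two non-THC sessions, 1 − (1 − p)² | At least one of six, 1 − (1 − p)⁶ |
|---|---|---|---|---|---|
| 6 h | 5 per year | 5 × 6/8760 = 0.3% | 0.4 | 0.7% | 2% |
| 6 h | 2 per week | 2 × 6/168 = 7.1% | 8.6 | 14% | 36% |
| 24 h | 5 per year | 5/365 = 1.4% | 1.6 | 2.7% | 8% |
| 24 h | 2 per week | 2/7 = 28.6% | 34.3 | 49% | 87% |

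**3. Effect on THC versus placebo.** The section on drugs and doses expects 30 mg THC to cost about 10 correct responses. I take the SD of the paired difference as 10/d, which is 11.5 for d = 0.87 and 10 for d = 1.0. Let own use cost e points in an affected session.

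*Additive residual (same cost in any condition).* The mean difference stays at 10, and the variance becomes (10/d)² + 2p(1 − p)e². With p = 2/7, e = 5 and d = 0.87, that is 132.1 + 10.2 = 142.3, so the SD is 11.93, the effective d is 0.838 and power is 94.4%. With e = 10, power is 89.7%.

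*Non-additive residual (lowers placebo only).* The mean difference becomes 10 − p × e and the variance (10/d)² + p(1 − p)e². Taking the extreme e = 10:

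- p = 2/7 (24 h): difference 7.1; power 69% (d = 0.87) to 79% (d = 1.0).
- p = 7.1% (6 h): difference 9.3; power 92% (d = 0.87) to 97% (d = 1.0).

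**4. Effect on THC versus THC + pinene.** The documents give no expected pinene effect. For an illustrative recovery of 5 points with the same SDs, power without residual is 45.5% (d = 0.87) to 56.5% (d = 1.0). With an additive residual of 5 points at p = 2/7 it is 42.9% to 52.5%, a loss of 3 to 4 percentage points. Placebo and pinene-alone sessions do not enter this contrast.

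**The case against.** A reader might infer that the crossover contrasts are contaminated and the comparisons biased. The documents do not support that. Order is randomized, each session has its own pre-dose cognitive test, and an additive residual leaves the mean differences unchanged. The fall to 7.1 points needs use at the entry cap, a 24-hour window, a residual as large as the whole 30 mg effect, and no effect on THC sessions.

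A reader might also take 29% as the share of sessions affected, or assume that the true rate lies between the tabulated rates. Neither follows. No passage supports 24 hours as the duration of effect, and even timing over the clock probably overstates use shortly before an arrival at about 8:00. Participants know that they are urine-tested and may abstain. In the other direction, the cap describes use before entry, and larger own doses could last longer.

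The THC exemption is itself reasonable. Study THC may have been given as little as 48 hours earlier, and a positive screen cannot tell it from own use.

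Some provisions could be read as cover. Exclusion criterion 3 lets the investigator exclude for interfering drugs or supplements within 14 days of sessions, and section 4.b allows a session to be repeated after a deviation affecting data integrity. The first is discretionary and does not name cannabis. The second is not clearly triggered, since own use breaches no stated rule. The removed consent pages may tell participants to abstain, so I claim no absence there. Such an instruction would still not supply an arrival action or an analysis rule.

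These arguments limit the likely damage. They do not fill the gap in the session procedures and the statistics section.

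**Conclusion.** The point holds as a gap in the session rule and the analysis plan, not as a demonstration of bias. A session in any condition can start after same-day or previous-night own use, and nothing says what to do at arrival or in the analysis.

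For the PASAT contrasts the likely consequence is modest extra noise: with an additive residual of up to 5 points, power for THC versus placebo stays at 94.4% or above even at the entry cap with a 24-hour window. A smaller THC-placebo difference needs a non-additive residual. The upward shift in absolute THC and metabolite levels, and the weaker balance for returning participants, remain whatever the form of the residual.

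The frequency is unknown. The ranges of 0.3% to 7% (6 hours) and 1.4% to 29% (24 hours) rest on entry-rate use continuing at random times. Residual sizes, alpha and sidedness are also assumptions.

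**What to change.** Keep the urine-THC waiver, and change three things.

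1. **Arrival check.** Add that TLFB-reported non-study cannabis use within one fixed window before the session leads to rescheduling. The investigators set its length, and it is the same for all six sessions, including those of returning participants.
2. **Discharge rule.** State whether a second positive urine screen exempts THC, so that it can be reconciled with the send-home rule.
3. **Analysis.** Prespecify:
   - (a) adjustment for each session's pre-dose PASAT;
   - (b) a sensitivity analysis of the PASAT contrasts that excludes, or adjusts for, sessions with TLFB-reported recent use;
   - (c) pre-dose correction of THC and metabolite pharmacokinetics.

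In (b), pre-dose plasma THC should be supporting evidence, read against the previous study dose, and not the sole flag. Samples are frozen and shipped, so they cannot decide whether a session starts. Nor do the documents show that they separate own THC from a study dose given 48 hours earlier; if they do not, the flag would partly track the preceding condition, and dropping flagged sessions would unbalance the crossover.

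The cost is a few sentences, since TLFB, pre-dose cognition and pre-dose blood are already collected. The downsides are some rescheduled sessions and possible under-reporting on TLFB once a report delays a paid visit.

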Study Measures. A battery of measures will be used to assess participant characteristics and drug effects during the study.

Screening. Initial study screening will be completed over the telephone. During the phone screening assessment, staff will conduct assessments to collect background demographic data (age, gender, self-reported race and ethnicity, height, and weight) and to determine study eligibility (e.g. Medical History Interview, Drug-History Questionnaire, Time Line Follow Back (TLFB) assessment of all substance use for the prior 90 days, self-report of adverse effects following cannabis use). If the volunteer appears eligible based on this interview, a physical examination will scheduled to be completed at the BPRU by medical staff. All major organ systems, including head, eyes, ears, nose, and throat (HEENT); cardiovascular system; lungs; abdomen (liver/spleen); extremities; skin; central nervous system (CNS); musculoskeletal system, and general appearance will be assessed. Biological specimens will be tested for routine clinical chemistry, hematology, serology, serum pregnancy test (females only), and for evidence of recent illicit drug use.

Experimental Sessions. Vital signs (heart rate, systolic blood pressure (SBP), diastolic blood pressure (DBP)) will be measured in the seated position using an automated monitor.

Six milliliters of blood will be collected by venipuncture or IV catheter insertion at baseline and again at the 0, 15, 60, 120, and 180-minute post-inhalation time points into vacutainer tubes. Blood will be spun to separate plasma, which will be labeled and stored frozen at -80 °C until

shipped frozen on dry ice to a designated laboratory for analysis. The maximum amount of blood to be collected is 36 mL per session, and 216 mL over the course of the 6 study sessions (226 mL including the screening visit), which is less than the amount typically collected during a single routine blood donation (473ml). Quantitative levels of THC and its metabolites (e.g. 11-OH-THC and THCCOOH) will be obtained. Additional analytical testing (e.g. markers of pinene) may be conducted as deemed appropriate to the current study.

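### The discharge rule sets no lower limit for blood pressure or heart rate and takes no standing reading: a small safety gap, cheap to close

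*Combined protocol and SAP*

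**What the plan says.** The release rule is in Section 4.a, Outpatient Discharge. It opens with a comparison when the session ends: "study staff will compare vital signs and cognitive performance assessments with baseline data". Release then depends on three conditions. One is ability to engage with staff. The vital-sign condition reads: "vital signs are within normative range (HR < 100bpm, SYS BP < 150mmHg, DIA BP < 90mmHg"). The third concerns cognitive scores, and the same sentence states what follows when all three are met: "performance is not below 20% of baseline, the participant will be cleared to leave without further evaluation".

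If a listed parameter fails, medical staff assess the participant and a field sobriety test is done. A further sentence deals with vital signs specifically: "If vital signs are out of range, then medical staff will evaluate and make a determination". That decision is between release and continued observation.

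Two safeguards rest on symptoms and behaviour. Staff are to "engage in face-to-face conversation with the participant to ensure that they are fit to leave the unit". There is also a hold for drug effects: "If the participant reports a drug effect or exhibits behavior indicative of impairment/intoxication, the participant will be asked to remain at the BPRU". The hold lasts while the effect persists. On travel, the rule is: "Participants will not be allowed to drive home".

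Section 4.a, Study Measures (Experimental Sessions), says that heart rate and blood pressure "will be measured in the seated position using an automated monitor". No standing reading is scheduled anywhere. Section 7.a names dizziness, change in blood pressure and orthostatic hypotension among the potential risks of THC.

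**The concern.** A release rule should be able to pick up the hazards that the protocol itself names. This one is built to catch high pressure and fast heart rate. It has no floor, so a low reading is not outside the printed range and leads to no stated action. Because readings are seated, a fall in pressure on standing does not appear in the range check or in the comparison with baseline. The text then clears the participant with no further evaluation.

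What is at stake is the safety of a participant who leaves with low pressure, or with a postural fall that nobody has noticed. No endpoint or analysis is involved.

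**Working it through.** The plan gives no figure to reproduce here. The check sets the sections side by side and then applies the printed rule to example readings.

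**Side by side**

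- Risks named (Section 7.a): change in blood pressure, orthostatic hypotension and rapid heart rate, among others.
- Limits for release (Section 4.a, Outpatient Discharge): HR < 100, SBP < 150, DBP < 90. There is no lower limit.
- Posture (Section 4.a, Study Measures): seated.
- Comparison with baseline (Outpatient Discharge): made at the end of the session, but no size of change is set and no action is tied to a fall.
- Other printed pressure limits (Section 5, inclusion criterion 7): 150 systolic and 90 diastolic at screening, again upper limits, so no floor can be borrowed from there.

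Rapid heart rate is covered by the limits. Low seated pressure and a postural fall are not.

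**The rule applied**

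Written vital-sign rule: pass if HR < 100 and SBP < 150 and DBP < 90. For contrast, the last column adds assumed floors of HR 50, SBP 90 and DBP 50, and an assumed postural limit of 20/10 mmHg. All readings and added limits are illustrative; the documents supply none of them.

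| Assumed reading before release | Written rule | With the assumed added limits |
|---|---|---|
| 120/75, HR 75 | passes | passes |
| 85/50, HR 75 | passes | review (85 < 90) |
| 70/40, HR 95 | passes | review (70 < 90; 40 < 50) |
| 110/70, HR 38 | passes | review (38 < 50) |
| 118/74, HR 80, falling 30/15 on standing | passes | review (30 ≥ 20; 15 ≥ 10) |
| 120/75, HR 105 | fails (105 ≥ 100) | fails |

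Of these six, the written rule stops only the high heart rate.

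**What the baseline comparison adds**

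Take an assumed baseline of 125/80.

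- *Low seated pressure.* A reading of 85/50 is a fall of 125 − 85 = 40 and 80 − 50 = 30 mmHg. Staff making the comparison would see it. What is missing is a stated threshold and action.
- *Postural fall.* A seated 118/74 is a change of 125 − 118 = 7 and 80 − 74 = 6 mmHg, which looks unremarkable. The standing value would be 118 − 30 = 88 over 74 − 15 = 59, and it is not taken.

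The first case is a gap in what the rule tells staff to do. The second is a gap in what is measured.

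**The case against.** The strongest reply is that the rule does not work alone.

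- Symptomatic hypotension can be caught. A participant who reports a drug effect such as dizziness, or who looks impaired, is kept on the unit, and the end-of-session conversation is meant to establish fitness to leave.
- Vital signs are taken at ten post-dose times, from 0 to 360 minutes (Section 4.a, Post-Drug Administration Procedures), so a seated fall would be in front of staff well before release.
- Inclusion criterion 3 requires good general health, including vital signs, without restricting this to high values. The exclusions cover significant illness, arrhythmia or vasospastic disease, interfering medication, and anemia or recent blood donation.
- Section 7.b provides nurses on site and a physician on call. One task in the cognitive battery includes balance. Observation lasts about six hours, which the protocol says has been adequate for similar doses.

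All of this stands, and it makes the remaining risk small. It does not supply a stated action for low seated pressure, and none of it measures pressure on standing. The word normative may suggest that a floor was intended, but none is printed.

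A reader might infer more than the text supports. One inference is that the plan cannot detect orthostatic hypotension at all. That is wrong: only a fall that is neither reported nor visible escapes. Another is that early leavers go without a vital-sign check. The items named for their medical review omit vital signs, but the next sentence requires the comparison with baseline at the end of each session, and nothing limits it to full-length sessions.

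A fair point on cost also stands. Adding floors to the existing list would send healthy people with naturally low pressure to a field sobriety test, so the fix should avoid that.

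**Conclusion.** The point holds as a low-severity safety improvement. The printed rule clears a participant with low seated pressure, and it does not measure a postural fall that is neither reported nor visible, although Section 7.a names both kinds of change as THC risks. This conclusion comes from the text alone; the example readings only illustrate it.

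The practical size cannot be quantified. The documents give no rate of postural hypotension and report no hypotensive event or release problem. A reader might infer that harm at release is likely, and nothing in the documents supports that. Multiplying sessions by participants would count opportunities rather than risk, and such a total may not hold for participants enrolled before the 15 mg pinene amendment. The case for change is that the fix is cheap.

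**What to change.** In Section 4.a, Outpatient Discharge:

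1. Add lower limits for heart rate and blood pressure, and a fall-from-baseline trigger, each leading to review by medical staff before release. The study's medical staff should set the values, with allowance for naturally low baseline pressure.
2. State that a low reading alone calls for medical review and does not by itself require the field sobriety test.
3. Take one standing reading before release, compare it with the seated end-of-session reading, and send a fall beyond a set size to medical review.

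Items 1 and 2 are wording, since the seated readings and staff are already in place. Item 3 uses the existing monitor and takes about two minutes per remaining session (assumed): 2 × 6 = 12 minutes for a participant with all six sessions to come, or 2 × 2 = 4 minutes for one returning only for the two added dose conditions. The downside is occasional extra observation or medical review. Endpoints, sample size and analysis do not change.
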